3C.1i. Evidence for Scientific Premise. SCD is a prevalent genetic disorder with significant public health impact. Pain is its hallmark symptom and accurate pain reporting is critical to effective care. High quality research has demonstrated that children can be accurate self-reporters of pain. Yet, barriers to effective communication between SCD youths and their care team (parents, providers, etc.) still exist. Children are high utilizers of technology; gaming approaches are not only popular but have demonstrated positive health behavior effects in the mHealth literature. Despite the encouraging evidence of “games for health”, the area of gamification for assessing pain, especially SCD pain, is remarkably underdeveloped despite promising results. Our proposal addresses gaps in the current literature, but is founded in strong preliminary evidence. Our Phase I research used a multi-method approach with input from key stakeholders and experts in the field. Using a user-centered design approach and social cognitive theory, we produced a functional prototype that was rated high for aesthetics and usability suggesting acceptability and feasibility of the product. Our Phase I outcomes provide strong preliminary evidence for moving forward with a full-scale production of the app.

FIGURE 5: Timeline

3C.2. Project Overview. The Phase II project will be conducted over 24 months (Figure 5). *Pinpoint* will be fully developed in Months 1-9 and evaluated for behavior change (i.e., increased communication skills) in Months 10-24 among a sample of teens with SCD aged 13-17 years. *Pinpoint* will be a web-based app that provides pain identification and assessment, and disease education. Using the user-centered design (UCD) approach from Phase I, usability testing will be conducted on newly programmed

features (n=14) and will guide final app development. A within-subjects design will enroll teens with SCD using a time series approach. Teens will be recruited from across the U.S. through SCD support groups and networks (see **Letters of Support**), and will use the app for 12 weeks. The primary outcome will be improvements in

communication skills regarding SCD. Teens (n=100) will complete baseline, 6-week, and 12-week assessments (Figure 7).

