3C.5. Experimental Design (AIM 3). AIM 3 will test the full *Pinpoint* app with 13-17 year olds with SCD (n=100) using a within-subjects times series design over 12 weeks to evaluate changes in (1) knowledge acquisition for communicating about pain and types of SCD pain; (2) the Pain Assessment Tool; (3) SCD general knowledge and self-efficacy, (4) family cohesion, and (5) app usage. The primary outcome measure (knowledge acquisition for communicating about pain and types of pain) will be developed. Change in knowledge acquisition for communication relative to baseline was chosen as the primary outcome because Phase I participants strongly expressed that improving communication skills and understanding their pain were the primary reasons why teens would use the app. In addition to teens being recruited, their parent will also be recruited to complete a parent proxy version of the primary outcome measure.

3C5.1. Trial Design (n=100). A within-subjects (repeated measures) design will be used. A number of designs were considered. A comparative-effectiveness trial was rejected since there is no existing app geared for SCD teens that could act as an appropriate comparator. A randomized controlled design was contemplated, and we considered a number of possible control conditions (e.g., no treatment control, waitlist control, etc.). However, we rejected the RCT concept due to resource demands for obtaining a large sample size for sufficient power (i.e., time and cost relative to a 24-month Phase II timeline), and input from the EAB and parents. Specifically, the EAB and parents believe parents would not be interested in participating if the possibility of a control condition was present. The purpose of a Phase II grant is to continue the research and development efforts initiated in Phase I and prepare it for commercialization. Our primary goals are to fully build the app and assess for individual improvements in communication and pain identification over time. Thus, a within-subjects design was chosen. The advantages of the within-subjects design are increased power with smaller sample size, and a reduction in error variance associated with individual differences. While the lack of a control group is a limitation, it was necessitated to overcome challenges in recruiting SCD teens experienced in Phase I. We will devote project resources to recruiting and retaining a sample in the treated group (i.e., receives *Pinpoint* app)

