that is sufficient to detect pre-post changes in primary and secondary outcomes rather than spend resources on securing a sample of which half will not be treated. We will also avoid having parents decline to participate due to the chance their teen will not receive the app. We have included two design aspects to control threats to validity¹⁴⁴: (1) we have a 6-week interim measure to create a time-series on the assessment of change; and (2) we will include a measure of communication and knowledge related to influenza as a nonequivalent dependent variable, which we do not expect will change pre to post as a result of the app despite it being subject to the same history, maturation, or regression threats as our primary and secondary measures. We will also include demographics, especially age of the teen and parental age and education, as covariates in the analysis as statistical controls against threats such as maturation.

A description of the app was provided in **Sections 3C.1d** and **3C.4.3c**. Participants will download the app following the procedures outlined in **Section 3C.7.1**. Project staff will provide users with a one-on-one app orientation and how to use its unique features via videoconferencing. Daily notifications will engage users in daily app use and provide up-to-date information on users' progress. Participant responses will also be used to evaluate additional or on-going support of users' needs. To protect privacy and to ensure that the participant is the person completing the app activities, KB will uniquely identify the user's smartphone/tablet based off the device's "hardware footprint". The app will upload all app activity data to the KB secured web server database.

3C.6. Target Population. There are two populations: teens with SCD and their parent. Inclusion criteria for teens are: (a) age 13-17 years; (b) diagnosed with SCD; (c) own a smartphone or tablet, and (d) read and speak English. Parents will be recruited to complete a parent proxy version of the primary outcome measure (child's knowledge acquisition; see **3C.7.2**), but will not use the app. Parent inclusion criteria are: (a) parent/guardian of eligible child and (b) able to speak and read English.

3C.7. Trial Conduct.

3C.7.1. Recruitment and Visit Procedures.

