Recruitment and Screening: Potential study participants will be recruited through nationwide SCD support groups, SCD networks, social media ads, and existing research participant databases. Recruitment was a challenge during Phase I due to IRB delays at the study hospital. Thus, we reached out to multiple national organizations to assist with Phase I recruitment. During Phase I, a number of organizations expressed interest in being a recruitment center for Phase II. We have four committed organizations and four others have expressed commitment via phone or email communication (see **Letters of Support**). In addition, we have the commitment of the EAB and PAB to assist with recruitment.

Participants will be sent an email describing the study and a link to an eligibility screening survey via KB's secure server. The online screener will take 5 minutes. Phone screening will be used as needed. Participants will receive an email informing them of eligibility. Eligible participants will be scheduled for an orientation/baseline visit which will be conducted via videoconferencing; a reminder email and text message will be sent 3 days prior to the assessment (similar reminders will be sent for 6- and 12-week visits).

Orientation and baseline/pre-test assessment: In a one-on-one orientation session to be conducted via videoconferencing, participants will have the study explained and provide written consent (parent) and assent (child). Immediately following, the teen will complete pre-test surveys online using their personal smartphone or tablet device (see **3C.8**) which should take about 30 minutes to complete. Parents will complete an online survey (proxy measure of the primary outcome). After the surveys, teens will be assisted with app download, provided instructions on how to use the app, and encouraged to use the app daily.

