For Aim 2 (Usability), 14 users are needed to identify any problems that impact $\geq 15\%$ of users at a 90% chance of detection ($\log(1-.90)/\log(1-.15)$). Data on applied formative research suggests that 5 participants is sufficient to identify likes/dislikes and potential errors; thus, the power to detect Level 1 severity usability errors should be more than sufficient with $n=14$.¹⁶⁷ Similar to Phase I, usability outcomes will also include program satisfaction ratings with regards to design, appeal, and functionality. Each concept will be rated on a 5-point Likert scale. Means will be calculated and an average of 67% or higher will be considered acceptable. We will examine mean scores, changes in mean scores, and variation within geographical location. The SUS will serve as the primary criterion for measuring usability.^{113,121,122} Further, we will look for outliers to assess if there may be specific characteristics of users who have or develop problems as the processes evolve.

Effectiveness (AIM 3) is critical to product development and will evaluate whether *Pinpoint* increases communication and pain identification knowledge. Means (standard deviations), medians (interquartile range), distributions, frequencies and percentiles will be used to characterize the primary outcome measure. We will test the within person change over time for knowledge acquisition, SCD disease-specific and transition knowledge, SCD self-efficacy, and family cohesion. Linear regression will assess the effects of age, **biologic sex**, and education. Parents will complete a proxy version of the primary outcome; child and parent-report agreement will be assessed using intra-class correlations and median difference tested using Wilcoxon significance tests. Kolmogorov-Smirnov tests will assess for normal score distribution.

Characteristics of dropouts and/or noncompliant individuals will be examined to shed light on potential weaknesses of the app (differential dropout overall or within certain subgroups). Utilization data will be examined to understand the acceptability and intensity of interactions with the app. The penetration of the app into this at-risk population is very important in understanding potential impact. Complier average causal effect models¹⁶⁸ will be used to examine the intensity of the app's utilization. Mediation models using the latest

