bootstrapping methods^{169,170} will be examined to provide evidence that the changes induced by the treatment effects are consistent with the changes being mediated via the app.

As a sensitivity analysis to demonstrate discordant validity, we will perform the same analysis as on the primary outcome, using the number of correct answers in the CDC Flu IQ (i.e., nonequivalent dependent variable). This outcome should not be impacted by the intervention and we expect to see no change in the mean number correct. Although failure to show a difference is not evidence for no difference, the discordant effect size should provide additional information that the primary results are consistent with an intervention effect.

Evidence for Scientific Rigor and Potential Limitations. The study has numerous strengths, few limitations, and is scientifically rigorous. The study is theory-driven (i.e., User-centered Design and Social Cognitive theories). Formative data will incorporate multiple stakeholder input. The programming approach will be multi-model and evidence-based (i.e., ADDIE Model, MDA framework, AGILE programming) resulting in a systematic, flexible, and cost-effective approach. Sample sizes are sufficient and supported by the literature. Effectiveness will be evaluated in a within-subjects design which allows for sufficient power (i.e., statistical inference with fewer subjects), efficiency (i.e., quicker trial completion), and longitudinal analysis (i.e., individual changes over time). The study team and environment are strong. Potential limitations are: (1) difficulty recruiting; (2) sources of bias; and (3) lack of control group. We have tried to reduce their impact. We will work closely with the EAB and PAB to maximize recruitment. Our primary outcome measure is new, but we are using a rigorous approach to scale development. Self-report instruments are open to bias, however the use of validated measures is a strength. Limitations of no control group are lessened via the use of a time-series design for outcome changes and testing of a nonequivalent dependent variable.

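### The SAP plans complier average causal effect models in a single-group trial where every teen gets the app, with no complier definition and no identifying assumption, so the complier effect is not identified as planned

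*Combined protocol and SAP*

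**What the plan says.** The complier plan is one sentence in the Analyses part of the SAP, under Aim 3. It names "Complier average causal effect models" and gives intensity of app use as their purpose. The next sentence adds bootstrap mediation models, meant to show that "changes induced by the treatment effects are consistent with the changes being mediated via the app".

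Section 3C5.1 describes one treated group. A randomised design was considered and rejected, and resources go to treated teens "rather than spend resources on securing a sample of which half will not be treated". The same section concedes the general point: "While the lack of a control group is a limitation".

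On measurement, section 3C.2 states: "Teens (n=100) will complete baseline, 6-week, and 12-week assessments". Section 3C.7.1 has every teen helped to download the app after the baseline surveys and "encouraged to use the app daily". Section 3C.7.2 (App Usage) logs use in detail but plans only summaries of it.

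On covariates, section 3C5.1 lists demographics, "especially age of the teen and parental age and education, as covariates in the analysis", and the SAP says "Linear regression will assess the effects of age", biologic sex and education.

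**The concern.** A complier effect compares what compliers showed with what the same people would have shown without the offer. Random assignment normally supplies that comparison. Here nothing is assigned and no substitute is named, so an extra assumption has to supply it, and the SAP states none. The SAP also leaves the complier class undefined, although its stated purpose, intensity, is a graded quantity.

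Followed as written, the plan would report an association between use and change under a causal name. Teens who are more motivated or better supported at home may both use the app more and learn more. The SAP treats effectiveness as central to product development, so a causal-sounding usage result could be given more weight than it can bear.

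The mediation sentence has a smaller version of the same fault. It names the app as mediator, which does not vary between teens, and it takes treatment-induced change as given.

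**Working it through.** **Plan's own figures.** The SAP attaches no number to the complier or mediation models, so there is none to reproduce. The one figure borrowed here is the expected number of completers: 100 × 0.80 = 80 (SAP, Sample size).

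**What a complier model needs, against what the documents give**

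| Needed | In the documents |
|---|---|
| Unexposed group or other instrument | None; all teens receive the app (3C5.1, 3C.7.1) |
| Complier definition | None. Daily use is encouraged, use is logged, and the SAP mentions noncompliant individuals without a threshold. The dummy variable in 3C.7.3 codes study completion, not app use |
| Identifying assumption | None stated |
| Pre-app trend to test such an assumption | Not available: of baseline, week 6 and week 12, only baseline precedes app use |

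**What the data can show.** Suppose a threshold is set and users are read from the logs. Let c be the app effect in users, s_u and s_n the change that users and non-users would show without the app, and e any effect of use below the threshold.

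- Users' own change = c + s_u
- Non-users' change = s_n + e
- Contrast = c + s_u − s_n − e

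Users' own change equals c only if s_u = 0. The contrast equals c only if s_u = s_n + e, for example a shared trend with no effect of sub-threshold use. Other routes are no confounding given covariates, or a trend shared with Flu IQ. This list is not exhaustive.

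**Illustration with assumed values** (c = 0.30 SD, e = 0; not figures from the documents)

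| s_u | s_n | Users' own change | Contrast |
|---|---|---|---|
| 0.10 | 0.10 | 0.40 | 0.30 |
| 0.10 | 0 | 0.40 | 0.40 |

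In the second row, where only users would have gained anyway, both estimates miss the true 0.30 by 0.10 SD, and their agreement gives no warning. Neither column changes with the share of users. The missing threshold matters in another way: it decides who counts as a user, and so which effect c is. At assumed shares of 40% to 80%, between 32 and 64 of the 80 completers would be users.

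**Precision of the replacement regression.** Inputs: n = 80; five covariates (baseline score, teen age, sex, parental age, parental education); two-sided 0.05 and 80% power, assumed because the SAP sets neither for this analysis.

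- Fisher z standard error = 1/√(80 − 3 − 5) = 0.1179
- Detectable partial correlation = tanh((1.960 + 0.842) × 0.1179) = 0.319

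**Precision if a user/non-user contrast is kept.** The SAP's before-after correlation of 0.5, which it gives for transition knowledge, makes the SD of change √(2 × (1 − 0.5)) = 1 score SD. With user share p, the standard error is √(1/(80p) + 1/(80(1 − p))) = 0.228, 0.228 and 0.280 at p = 0.4, 0.6 and 0.8. The detectable difference (noncentral t, 78 df, same alpha and power) is 0.65, 0.65 and 0.79 SD.

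**The case against.** The strongest defence is that the plan is open about its limits. It admits the missing control group in 3C5.1 and in both statements of limitations. It adds a 6-week measure and the Flu IQ quiz against history, maturation and regression, and it calls its analyses mainly descriptive. The complier model carries no alpha, and its stated purpose is usage intensity, not efficacy. All of this stands, and it limits the weight of the point. It does not remove it: neither safeguard is tied to the complier model, and neither deals with motivated teens both using the app more and learning more. A descriptive aim also sits badly with a causal label.

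Four stronger readings should not be drawn:

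- A reader might infer that the effect must be estimated as in a randomised trial, by dividing mean change by the share of users, and so would be inflated when few teens use the app. That division is needed when compliers cannot be seen. Here use is logged for every teen, so under no change without the app, users' own mean change is the direct estimator.
- A reader might infer that only two assumptions are possible. The Flu IQ reasoning in 3C5.1 and the SAP comes close to offering another, though it is not linked to compliers.
- A reader might infer that the method has no source, because its citation number, 168, exceeds a reference list ending at 165. The SAP's numbers appear to run five ahead of the list: its mediation citations, 169 and 170, fit entries 164 and 165. What entry 163 assumes cannot be seen here, and it could not supply a threshold for this app.
- A stray phrase in 3C.7.3 hints at two assigned apps, but 3C5.1 and 3C.7.1 plainly describe one group.

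**Conclusion.** The point holds for this secondary analysis. With every teen given the app, no instrument, no usage threshold and no stated assumption, the complier effect is not identified as planned. An added assumption could identify it, but one measurement before app use gives no pre-app trend with which to test that assumption.

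The documents give no figure for the size of the possible bias. The 0.10 SD error in the illustration is simply the assumed change without the app.

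A reader might infer that the trial's main result is undermined. This point does not support that: no alpha, power or decision rule depends on the complier model, and the primary within-person test is unaffected. The mediation wording is a minor matter, since the SAP claims only consistency with mediation. The plan should be corrected, but the trial does not depend on it.

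**What to change.** Before usage data are examined, replace the complier sentence with a pre-specified exploratory analysis:

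1. Fix one usage measure from the logs, such as total minutes or modules completed over 12 weeks.
2. Regress 12-week change in the primary score on it, adjusting for baseline score, teen age, biologic sex, and parental age and education.
3. Run the same model on Flu IQ change as a partial negative control. An association would point to confounding. A null result is weak reassurance, because motivation that acts through learning about sickle cell disease need not move flu knowledge.
4. Report both as associations open to confounding by motivation, without the words causal effect.

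If a complier model is kept, state the usage threshold and the identifying assumption in advance, and report the result as conditional on that assumption. In the mediation sentence, name logged app use as the mediator and label the result an exploratory association.

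The cost is a change of SAP wording and two regressions on data already planned. The sponsor gives up the causal label. The replacement is no better protected against confounding by motivation, and its power is limited as shown above. The gain is an accurate label, a usage measure that cannot be tuned to the result, and a partial check.

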3C.4.3c. Development of New Components. The *Pinpoint* app will focus on helping SCD teens build practical and constructive communication skills and providing them with a platform for practice and feedback. Examples of communication content areas include nonverbal communication, self-disclosure, expression of emotions, trust, mutual respect, empathy, conflict management, and coping strategies. Consistent with research on mHealth strategies for adolescents,¹²⁶⁻¹³⁰ the proposed design emphasizes gaming as a teaching strategy. These interactive components will be the centerpiece of the app. Outcomes of each game will be used to ensure uptake of information (e.g., users must achieve a targeted score or level to demonstrate comprehension to receive a reward), thus providing feedback to participants early and often. To reinforce learning and bolster adherence, “badges” (i.e., visual icons), will be awarded intermittently. Badges are highly effective gaming tools used to encourage user engagement and build game “loyalty”.¹³¹⁻¹³⁴

Details of components programmed in Phase I were provided in **Section 3C.1d** and **Figure 4**. Three modules were programmed in Phase I and will be refined and expanded in Phase II. Two additional modules will be built from scratch: Daily Pain Journaling and Resources for Parents, Providers, and Teens; each module will contain multiple sections. Based on Phase I feedback, the app will use an avatar to help guide and provide modeling and instruction to the user. Teens will be asked to set pain management goals (e.g., methods to maintain health,

FIGURE 6: SCT with Tina, the Learning Buddy
Tina is a learning buddy that follows the user throughout the game. Interactions with Tina are used to integrate the ideas of SCT, such as modeling behavior, providing support, and encouraging user to reach pain management goals. During registration, the user chooses Tina as her learning buddy from a menu of many learning buddies.

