Knowledge Acquisition (Communicating about pain and SCD pain knowledge): The primary outcome measure will be developed for this project in collaboration with the EAB, and psychometric properties for will be evaluated (e.g., content-validity, criterion-related validity, construct validity, and internal consistency) using a 3-step scale development process: (1) domain identification and item generation; (2) content expert validation, and (3) pilot test.¹⁴⁵ The investigative team will generate items using a sorting process that encompasses themes/construct elements noted in the communication (nonverbal communication, self-disclosure, expression of emotions, trust, mutual respect, empathy, conflict management, and coping strategies) and pain identification literature (Step 1). Items will then be subjected to expert validation by the EAB (Step 2),¹⁴⁵ who will identify and delete theoretically incoherent items thus ensuring that the items in the instrument demonstrate content validity. Specifically, the EAB will sort the items by “how much” each item measures its targeted construct. The comprehensiveness of the entire instrument will be evaluated by identifying items which the EAB perceives to be incongruent with its nominated domain. The EAB will then be asked to identify the clarity of each item’s construction and wording to ensure that there are no ambiguous and poorly written items. Lawshe’s Content Validity Ratio (CVR)¹⁴⁶ will be utilized to assess the content expert judgment; a minimum CVR value of 0.49 will be required for retention in the scale.¹⁴⁶ For Step 3, usability testers (see AIM 2) will be asked to complete the measure to guide preliminary psychometric evidence and allow for revision of the instrument prior to launching in the full study. Reporting of internal consistency reliability is a necessary part of scale development.¹⁴⁷ Cronbach’s coefficient alpha of .70 is the suggested minimum.¹⁴⁸ All the factors’ intercorrelations will be calculated and should be less than 1.00 to be conceptually distinct. To allow precision in evaluating the new measure, confirmatory factor analyses (CFA) will be conducted. Exploratory factor analysis (EFA) may be required depending on the results of the CFA. The overall purpose of exploratory and confirmatory factor analyses will be to ensure the stability of the factor structure.

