services. It is designed to assess SCD knowledge in seven areas: (1) pathophysiology, (2) genetics, (3) physical symptoms, (4) treatment, (5) self-care, (6) psychosocial and developmental issues, and (7) health care delivery. It has good psychometric properties.^{153,154} Higher scores represent greater knowledge.

Sickle Cell Self-efficacy Scale: This instrument, used to assess self-efficacy in adolescents with SCD,¹⁵⁵ is comprised of nine questions measuring participants' perceptions of their ability to function on a day-to-day basis and to manage SCD symptoms (e.g., pain). The instrument is reliable and valid for assessing adolescents' self-efficacy for engaging successfully in day-to-day activities despite having SCD.

Family Cohesion: Family cohesion will be assessed by the single item Family Cohesion scale from the Child Health Questionnaire (CHQ)¹⁵⁶, a pediatric quality of life (QOL) survey that has been normed for children age 5 to 18 years including those with chronic diseases. The CHQ consists of 28 items that assess 14 different concepts regarding child and family physical and psychosocial well-being. There is evidence of good reliability and validity of this measure¹⁵⁶ including the single-item Family Cohesion question.¹⁵⁷ This scale, which rates a family's ability to get along with one another, uses a single item ("In general, how would you rate your family's ability to get along with one another?") rated on a 5-point scale. The PAT is assessing QOL, therefore to reduce duplication of information and study burden only the Family Cohesion item will be administered.

CDC Flu IQ measure: This is a 10-item quiz developed by the Centers for Disease Control to assess general knowledge about influenza and vaccination. It will serve as a nonequivalent dependent variable.

App Usage: App use will be monitored using Web Trends software; tracking macro and micro level data. It will record how users move through the program including the time spent on each activity, response latency to individual items, and scores achieved on games. Summaries of these data (means, ranges) will be reviewed to understand usage patterns. Teens will be sent "push notifications" to encourage app use. Users will evaluate the app on the **System Usability Scale** at the 6- and 12-week assessment.¹⁴²

3C.7.3. Adherence, Dropouts, and Participant Compensation.

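### With every teen given the app, the planned mediation analysis can only estimate a usage-outcome association, and its undefined mediator may include game scores that test the outcome itself

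*Combined protocol and SAP*

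**What the plan says.** The SAP (Analyses, AIM 3) says that bootstrapped mediation models will be used "to provide evidence that the changes induced by the treatment effects are consistent with the changes being mediated via the app". It names no mediator, no independent variable and no outcome model for this analysis. Utilization data are mentioned just before, for a different purpose: judging acceptability and intensity of use.

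The one planned measure of app use is App Usage (protocol 3C.7.2), which logs how users move through the program, "including the time spent on each activity, response latency to individual items, and scores achieved on games". Section 3C.4.3c explains what a game result means: "Outcomes of each game will be used to ensure uptake of information (e.g., users must achieve a targeted score or level to demonstrate comprehension". The same section gives the app's topics: "Examples of communication content areas include nonverbal communication, self-disclosure, expression of emotions, trust, mutual respect, empathy, conflict management, and coping strategies". Section 3C.7.2 generates the communication items of the primary questionnaire from the same list, "nonverbal communication, self-disclosure, expression of emotions, trust, mutual respect, empathy, conflict management, and coping strategies", and adds pain identification. The Vocabulary Game (3C.1d) is a timed match of pain words to definitions.

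Section 3C5.1 sets a within-subjects design with no control group. Every teen receives the app after the baseline survey.

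**The concern.** Mediation analysis splits a treatment effect into a part that passes through a mediator and a part that does not. Here treatment does not vary between teens, so there is no comparator for the first path. What remains is whether teens who used the app more also changed more. Motivation or prior knowledge could produce that pattern without any teaching by the app.

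The second difficulty is what usage might mean. A game score is close to a second test of the outcome. Teens who already know more tend to score higher in the games and at post-test, and adjusting for one imperfect baseline test does not remove this. If scores enter the mediator, knowledge is partly being correlated with knowledge.

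At stake is how the result is read. The trial has no control group, so a statement that change ran through the app would be taken as attribution.

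**Working it through.** The documents give no figure for the mediation analysis, so there is none to reproduce.

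**Step 1: the treatment-to-mediator path.** Usage before download is zero for everyone. In a within-person mediation model the first path is then a = mean(usage) − 0, which is positive by construction. The indirect effect a × b differs from zero exactly when b does, and b is the usage-outcome slope. This holds for any usage variable.

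**Step 2: a score-based mediator when the app does nothing.**

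Inputs from the documents:
- Completers: 100 × 0.80 = 80 (SAP, Sample size).
- Before-to-after correlation 0.5 (SAP, Sample size; stated for transition knowledge).
- Minimum Cronbach's alpha 0.70 for the new questionnaire (3C.7.2). This is internal consistency, borrowed here as a reliability.

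Assumptions not in the documents:
- Test reliability ρ of 0.5 to 0.7. With stable knowledge, ρ is also the pre-post correlation.
- Game-score reliability g of 0.3 to 0.7.
- Correlation λ of 0.5 to 1.0 between the trait behind the games and the trait behind the questionnaire.
- Two-sided α of 0.05.

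The correlation of either test with the game score is r = λ√(ρg).

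Baseline-adjusted model: the partial correlation of post-test with game score, given baseline, is r(1 − ρ) / √[(1 − ρ²)(1 − r²)].
- ρ = 0.7, g = 0.7, λ = 1: r = 0.70, giving 0.70 × 0.30 / √(0.51 × 0.51) = 0.21 / 0.51 = 0.41.
- ρ = 0.7, g = 0.3, λ = 0.5: r = 0.5 × √0.21 = 0.229, giving 0.229 × 0.30 / √(0.51 × 0.9475) = 0.0687 / 0.695 = 0.099.

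Change-score model: baseline and post-test have the same correlation r with the game score, so the difference has correlation 0 with it.

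Rejection rates (%) for the game-score slope in the baseline-adjusted model (no app effect, n = 80, 20,000 simulated trials per cell):

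| ρ | g | λ = 0.5 | λ = 0.7 | λ = 1.0 |
|---|---|---|---|---|
| 0.5 | 0.3 | 17.6 | 30.9 | 58.4 |
| 0.5 | 0.5 | 26.0 | 48.6 | 85.8 |
| 0.5 | 0.7 | 35.5 | 66.0 | 97.9 |
| 0.7 | 0.3 | 14.2 | 24.0 | 48.6 |
| 0.7 | 0.5 | 20.7 | 39.4 | 79.4 |
| 0.7 | 0.7 | 28.2 | 56.2 | 97.0 |

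In all 18 settings the change-score model rejects in about 5%.

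**Step 3: the bootstrap the SAP plans.** With ρ = 0.5 and λ = 1, the 95% percentile interval for a × b excludes zero in 63%, 86% and 98% of null trials at g = 0.3, 0.5 and 0.7 (baseline-adjusted). With a change score it does so in 4.5 to 7%.

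**Step 4: other cases (λ = 1).**
- An equal mix of game score and time, baseline-adjusted, with ρ widened to 0.5 to 0.9: 13 to 69%.
- Change score, score-only mediator, with knowledge drifting for reasons other than the app (assumed mean 0.3 SD, individual SD 0.3 to 0.5): 7 to 54%.
- Time only, assumed independent of knowledge: 4 to 7% in either model.

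**The case against.** The strongest reply is that the documents never make game scores the mediator. A reader might infer that they do, and that the analysis will report mediation in nearly every trial. Neither inference is supported. The mediator is unnamed, and utilization data have their own stated purpose. Section 3C.5 defines the primary outcome as change from baseline, the SAP tests within-person change, and the covariates listed are demographics. The model closest to that text is a change score, for which the rate is about 5% when knowledge is stable. The 97 to 98% figures also need a perfectly shared trait. Timed play, and replay to reach a target score, could make game scores partly a record of exposure. All of this stands.

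It is also fair that mediation is not the trial's central claim. That rests on within-person change, supported by the 6-week measure and the Flu IQ comparison. The SAP calls its analyses largely descriptive, claims only consistency with mediation, and acknowledges the missing control group.

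These replies do not settle two matters. The lack of contrast needs no argument about game scores. And the SAP does not commit the mediation model to a change score or keep scores out of it, so the error rate depends on choices still open when the data arrive.

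**Conclusion.** The concern holds in two parts. First, by design, the mediation models cannot provide evidence that change was mediated via the app. They estimate an observational usage-outcome association, whichever usage variable is chosen.

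Second, because mediator and model are undefined and the usage log contains comprehension scores, spurious mediation is possible, though not inevitable. With no app effect and n = 80, its rate is about 14 to 98% under baseline adjustment over the assumed ranges, and about 5% with a change score and stable knowledge. It can rise above 5% with a change score if knowledge drifts for other reasons. These rates rest on reliabilities, a latent correlation and a drift that the documents do not give.

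The matter should be corrected because it changes what the trial may conclude. It does not undermine the primary test of within-person change.

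**What to change.** In the SAP (Analyses, AIM 3) and protocol 3C.7.2:

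- Replace the mediation statement with an exposure-response analysis: change score from baseline to week 12, and from baseline to week 6, on usage defined in advance as sessions, active minutes and modules opened.
- Report game scores, levels, badges and latency as process outcomes only, barred from any exposure or mediator variable.
- Run the same model on Flu IQ. This is a partial check on general motivation. It covers a different subject, so it cannot detect overlap between game scores and sickle cell knowledge.
- Describe the result as an association open to confounding, not as evidence of mediation.

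A lagged test of early usage against change from week 6 to week 12 should not be substituted. If a real gain is complete by week 6 and maintained, the later change contains no usage effect, and the test rejects only at its nominal 5%. If part of the gain fades, the slope turns negative.

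The cost is SAP wording and a different summary of data already logged. The downside is a weaker claim.
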